### **11.3      Risks and Benefits of Study Procedures**

#### **11.3.1    Swabbing Procedures**

There are minimal risks to the participant who receives nasopharyngeal, conjunctival, and buccal swabbing. Participants may experience some temporary discomfort, but the swabbing involves minimal risk. Any adverse effects, such as nosebleeds, will be treated immediately by the examiners. Other health care will be provided at no cost to the study participant if necessary to address a study-related adverse health event.

#### **11.3.2    Antibiotic Frequency**

There are minimal risk of antibiotic resistance developing within the participant depending on how frequent they are instructed to take antibiotics. This will be rare, however, as all moxifloxacin regimens are commonly used in current practice.

## **Chapter 12: Study Monitoring**

The project will be continuously monitored by the study team.

## **Chapter 13: Data and Safety Monitoring Committee Charter**

This Charter is for the Data Safety and Monitoring Committee (DSMC). The Charter will define the primary responsibilities of the DSMC, its relationship with other trial components, its membership, and the purpose and timing of its meetings. The Charter will also provide the procedures for ensuring confidentiality and communication, statistical monitoring guidelines to be implemented by the DSMC, and an outline of the content of the Open and Closed Reports that will be provided to the DSMC.

### **13.1 Primary Responsibilities of the DSMC**

The DSMC will be responsible for safeguarding the interests of trial participants, assessing the safety and efficacy of the interventions during the trial, and monitoring the overall conduct of the trial. The DSMC will provide recommendations about stopping or continuing the trial. To contribute to the integrity of the trial, the DSMC may also formulate recommendations relating to the selection/recruitment/retention of participants, protocol-specified regimens, and the procedures for data management and quality control.

The DSMC will be advisory to the trial leadership group, hereafter referred to as the Steering Committee (SC). The SC will be responsible for promptly reviewing the DSMC recommendations and determining, whether to continue or terminate the trial, and to determine whether amendments to the protocol are required. If needed, the DSMC may seek the advice of a content expert outside of the committee.

### **13.2 DSMC Membership**

The DSMC is an independent multidisciplinary group consisting of epidemiologists, biostatisticians, and clinicians that collectively has experience in the conduct and monitoring of randomized clinical trial.

### **13.3 Conflicts of Interest**

The DSMC membership has been restricted to individuals free of apparent conflicts of interest. The source of these conflicts may be financial, scientific, or regulatory. Thus, neither study investigators nor individuals employed by the

---

ARIES Study

Manual of Operations and Procedures

sponsor, nor individuals who might have regulatory responsibilities for the trial products, are members of the DSMC.

The DSMC members will disclose to fellow members any consulting agreements or financial interests they have with the sponsor of the trial, with the contract research organizations (CRO), or with other sponsors having products that are being evaluated or that are competitive with those in the trial. The DSMC will be responsible for deciding whether these consulting agreements or financial interests materially impact their objectivity.

The DSMC members will be responsible for advising fellow members of any changes in any of the membership requirements that occur during the course of the trial. It may be appropriate for DSMC members who develop significant conflicts of interest resign from the DSMC.

DSMC membership is to be for the full duration of the trial. If any members leave the DSMC, the SC, in consultation with the DSMC, will promptly appoint a replacement.

#### **13.4 Timing and Purpose of the DSMC Meetings**

##### **Organizational Meeting**

The initial meeting of the DSMC will be an Organizational Meeting. This is during the final stages of protocol development and the purpose is to provide advisory review of scientific and ethical issues relating to study design to discuss the standard operating procedures and to discuss the format and content of the Open and Closed Reports that will be used to present trial results.

The Organizational Meeting will be attended by all DSMC members, lead trial investigators, and the trial biostatistician. The DSMC will be given the drafts of the trial protocol, the Statistical Analysis Plan, the DSMC Charter, and the current version of the case report forms. At subsequent meetings, committee members will receive Open and Closed Data Reports.

##### **Formal Interim Analysis Meetings**

There will be no planned interim analysis given this is a small trial.

### **13.5 Procedures to Ensure Confidentiality and Proper Communication**

To enhance the integrity and credibility of the trial, procedures will be implemented to ensure the DSMC has access to all emerging information from the trial regarding comparative results of efficacy and safety, aggregated by treatment arm.

#### **Closed Sessions**

Sessions involving only DSMC members and, where appropriate, those unmasked trial investigators (on the Data Coordinating Committee) who generate the Closed Reports (called Closed Sessions) will be held to allow discussion of confidential data from the trial, including information about the relative efficacy and safety of interventions.

At a final Closed Session, the DSMC will develop a consensus on its list of recommendations, including that relating to whether the trial should continue.

#### **Open Session**

In order for the DSMC to have access to information provided, by study investigators, or members of regulatory authorities, a joint session between these individuals and DSMC members will be held between the Closed Sessions.

#### **Open and Closed Reports**

For each DSMC meeting, Open and Closed Reports will be provided. Open Reports will include data on recruitment and baseline characteristics, pooled data on eligibility violations, and completeness of follow-up and compliance. The study statistician ([name]) will prepare these Open Reports.

Closed reports, available only to those attending the Closed Sessions of the meeting, will include analyses of primary and secondary efficacy endpoints, including subgroup and adjusted analyses, AEs and symptom severity, and Open Report analyses that are displayed by intervention group. These Closed Reports will be prepared by the study biostatistician.

The Open and Closed Reports should provide information that is accurate, with follow-up that is complete to within two months of the date of the DSMC meeting. The Reports should be provided to DSMC members approximately three days prior to the date of the meeting.

### **Minutes of the DSMC Meeting**

The research team will prepare minutes for the open portion of the meeting, including the DSMC's recommendations.

### **Recommendations to the Steering Committee (SC)**

At each meeting of the DSMC during the trial, the committee will make a recommendation to the Steering Committee to continue or terminate. This recommendation will be based primarily on safety and efficacy considerations and will be guided by statistical monitoring guidelines defined in this Charter.

Recommendations to amend the protocol or conduct of the study made by the DSMC will be considered and accepted or rejected by the SC. The SC will be responsible for deciding whether to continue or to stop the trial based on the DSMC recommendations.

The DSMC will be notified of all changes to the protocol or to study conduct. The DSMC concurrence will be sought on all substantive recommendations or changes to the protocol or study conduct prior to implementation.

The SC may communicate information in the Open Report to the sponsor and may inform them of the DSMC recommended alterations to study conduct or early trial termination in instances in which the SC has reached a final decision agreeing with the recommendation. The SC will maintain confidentiality of all information it receives other than that contained in the Open Reports until after the trial is completed or until a decision for early termination has been made.

#### **13.6 Statistical Monitoring Guidelines**

The SC will propose statistical rules for a futility stopping rule and an efficacy stopping rule at the first DSMC meeting.

## **Chapter 14: Data Collection, Management, and Security**

### **14.1 Scope of Data**

Genetic data will be collected in this trial from specimen collection.

### **14.2 Data Storage, Management, and Security**

Data will be recorded electronically using an encrypted and secure Excel spreadsheet and REDCap, which can securely store confidential information. Only people on the study team will have access to the information.

### **14.3 Data Monitoring and Cleaning**

Data monitoring and cleaning will be overseen by the data coordinating center (DCC) at the coordinating site. Data collection will be monitored on a weekly basis by the study coordinator using the dashboard function on REDCap.

## Appendix

Appendix 1. SAP

Appendix 2. Instructions for self-sample collection

Appendix 3. DEQ-5 Questionnaire

Appendix 4. SPEED Questionnaire

## Appendix 2. Instructions on Self-Collected Rectal Samples

## ARIES Instructions on Self-Collected Rectal Samples

Thank you for providing a rectal sample. Your sample will help the researchers at the University of California, San Francisco better understand how topical antibiotic use affects antibiotic resistance in the gut.

- 1 Wash hands with soap and water. Dry hands thoroughly and put on the provided gloves from the kit.
- 2 Loosen but do not remove the cap of the collection tube labeled "RECTAL".
- 3 In a private location, open the Sterile Flocked Collection Device and remove the swab from its wrapper without touching the soft, cotton tip.
- 4 Hold the swab between your thumb and forefinger so that you have good control.
- 5 With one foot on the edge of the toilet bowl, pull back your left buttock with your left hand.
- 6 Gently insert the tip of the swab into your anus about 1 to 3 cm.
- 7 Rotate the swab 360 degrees at least twice. Gently remove the swab from your anus. It should be a brownish color.
- 8 Place the soft tip of the swab into the container and break off the swab using the pre-scored breaking point.
- 9 Close the specimen container carefully and ensure the lid is fully secured. Gently stretch the Parafilm (arrow) around the seal to prevent tube leakage.
- 10 Dispose of the gloves in the trash and thoroughly wash your hands.

Version 1 (November 24, 2020)

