#### **Inclusion Criteria:**

1. Over 18 years of age
2. Undergoing cataract surgeries that would benefit from intracameral antibiotics
3. Able to provide swabs
4. Able to provide consent
5. Surgery of the second eye occurs at least 8 weeks after surgery of the first eye

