### **Specimen Collection**

All participants will have NP swabs, conjunctival swabs, and buccal swabs collected by the study doctors or study coordinator. Rectal swabs will be collected by the patient themselves by following instruction guide (see Appendix).

All specimens will immediately be placed in a Zymo preservative after collection and labeled with the participant's study number. Samples will then be transported to the Heintz laboratory at [name] for long-term storage at -80C and processing.

Conjunctival swabs will be collected prior to surgery. Conjunctival, NP, buccal, and rectal swabs will be collected 1-Week post-op. Conjunctival, NP, and buccal swabs will be collected 4-Week post-op.

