## **Chapter 7: Specimen Collection for Resistance and Microbiome Testing**

### **7.1 Participants**

We will collect nasopharyngeal, conjunctival, buccal, and rectal swab samples from all 108 participants. The swabbing will occur prior to surgery (conjunctival), 1-week post-op (conjunctival, NP, buccal, rectal), and 4-Week post-op (conjunctival, NP, buccal). The enrolled participants will be given instructions on when and where to go for swabbing visits after surgery.

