#### **7.2.4 Rectal Swabs:**

The test will require that the participant themselves to obtain a good sample. It is important to describe the test to the participant thoroughly to ensure a good sample is taken. The rectal swabs include an instruction guide (see Appendix) with the following instructions:

1. Put on a clean pair of gloves.
2. Partially open the fecal swab package and remove the top section of the collection vial (this can be discarded).
3. Remove the swab from the package. Take care that the cotton tip is not touched. If it is touched, throw the swab away and begin with a new one.
4. Insert the tip of the swab into your anus only as far as needed to contact fecal material (1-3cm) and rotate 180 degrees. The tip should be a brownish color when removed.
5. Place swab into the preservative in the collection tube. Make sure the swab is fully submerged in the liquid preservative and then break the swab off using the pre-scored breaking point.
6. Screw the cap back on the tube and make sure that it's tightened. Wrap the area where the cap meets the tube with Parafilm to ensure that the sample will not leak, and then place the tube into the appropriate sample box.
7. If the swab cannot be broken off while the tip is fully submerged in the liquid, try twirling the swab in the liquid first (to release the contents of the sample into the preservative) before breaking it off. Avoid rubbing the

sample on the tip of the swab off on the side of the tube where there is no liquid.

8. Hand the tube with the sample to the investigator/study coordinator.
9. The investigator/study coordinator places the number label on the collection tube.
10. Tube will be stored at -80C until sample processing.

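### The rectal self-swab sheet sets a one-foot-raised position with both hands in use one week after cataract surgery, differs from section 7.2.4, and concerns a swab that the risk section omits

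*Combined protocol and SAP*

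**What the plan says.** The texts below stand in both documents with no difference that matters here.

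- **Who and when.** Section 7.1: "We will collect nasopharyngeal, conjunctival, buccal, and rectal swab samples from all 108 participants". Chapter 5, Specimen Collection: "Conjunctival, NP, buccal, and rectal swabs will be collected 1-Week post-op". The pre-operative and 4-week visits have no rectal swab. It is the only one of the four that participants take themselves.
- **Participant sheet (Appendix 2).** Step 3 sends the participant somewhere private. Step 4: "Hold the swab between your thumb and forefinger so that you have good control". Step 5: "With one foot on the edge of the toilet bowl, pull back your left buttock with your left hand". Steps 6 and 7 are insertion and rotation.
- **Manual (section 7.2.4).** It introduces its own list with the words "The rectal swabs include an instruction guide (see Appendix) with the following instructions". That list sets depth and rotation but no body position.
- **Risks (section 11.3.1).** "There are minimal risks to the participant who receives nasopharyngeal, conjunctival, and buccal swabbing". The section goes on: "Participants may experience some temporary discomfort, but the swabbing involves minimal risk". Its one example of an adverse effect is a nosebleed.

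**The concern.** The swab serves research only and has no part in the patient's treatment. It is taken by people who had eye surgery a week before, and the sheet gives them a single way to do it, in a position that looks unsteady. The eligibility criteria set no upper age limit and no requirement on mobility or balance. If the position is not needed for a good sample, the study adds a risk for no return, and a fall during the procedure would be a study-caused safety event.

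There is a smaller cost in data. Someone who cannot or will not take the position may hand in no rectal sample, and no later visit offers a second chance. Separately, if the sheet and the manual describe the same swab differently, samples may not all be taken in the same way.

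**Working it through.** No figure in the plan needs reproducing and no power or error-rate calculation applies. The check compares the texts and counts exposures.

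**1. Are both hands in use?** Step 4 puts the swab in one hand. Step 5 assigns the left hand to the buttock. No step between there and the end of rotation in step 7 frees either hand. So neither hand is available for support while one foot is on the rim.

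**2. Does the sheet offer a way out?** None of its ten steps gives another position, advises support or mentions balance. It also fixes the left hand, whichever hand the participant would prefer to use.

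**3. Is the position needed?** Setting the two descriptions of the same swab side by side:

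| Item | Section 7.2.4 | Appendix 2 |
|---|---|---|
| Body position | none stated | one foot raised, left hand on buttock |
| Depth | 1 to 3 cm | 1 to 3 cm |
| Rotation | 180 degrees | 360 degrees, at least twice |

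The depth agrees. The position appears only in the sheet, and neither document links it to sample quality. The manual's own description does without it, which is the ground for calling the risk avoidable. The rotation differs by a factor of at least four: 2 × 360 = 720 degrees against 180. The two texts therefore disagree on posture and on rotation, although section 7.2.4 presents its list as the content of the guide.

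**4. Does the risk section cover this swab?** Section 11.3.1 names three swab types and the plan collects four. The rectal swab is the one left out. The section relies on examiners to treat adverse effects at once, but for this swab the participant is in private.

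**5. Would a fall be recorded?** The active survey (section 10.6.2) consists of two eye-symptom questionnaires, and at the 1-week visit it is completed before specimens are taken. A fall during the swab would reach the record through participant report under section 10.6.1 or because staff noticed it, not through the survey.

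**6. Exposure.** 3 arms × 36 = 108 participants; 108 × 1 rectal swab = up to 108 self-collections. This counts procedures, not events.

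**7. What a missed swab costs.** Rectal samples per participant: 1. Other non-ocular samples per participant: nasopharyngeal and buccal, each at 1 and 4 weeks, so 2 × 2 = 4. Losing the rectal swab removes that person's gut result and leaves four samples that still bear on Objective 2.

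**The case against.** Several objections are fair.

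- **Disclosure.** A reader might infer that participants are not told of this risk. The documents do not support that. The consent pages were removed before review, and Chapter 11 says the written consent will cover every study activity involving patient contact. Section 7.2.4 also tells staff to explain the test thoroughly, though for the sake of sample quality. All that can be said is that the protocol's own risk section omits the swab.
- **Standing on one leg.** A reader might take this to be the instruction. The sheet never says to stand, and a foot on the rim is itself a point of contact. Balancing mainly on the other leg is a reasonable inference from the wording, but it is an inference.
- **Ability to give a sample.** Inclusion criterion 3 requires that participants can provide swabs, and anyone may withdraw. This lowers the chance of missing samples. It is not a safeguard for balance, because the criterion says nothing about how the swab is taken.
- **Staff nearby.** The tube is handed to the investigator or coordinator, so help is close even though the participant is in private. Section 11.3.1 also promises free care for study-related harm. Both soften the consequences of a fall but do not prevent one.
- **Objective 2.** It would be wrong to infer that a missed rectal swab removes the participant from Objective 2, since four other non-ocular samples remain.
- **Effect of posture on the sample.** One cannot argue that posture is irrelevant because depth and rotation are fixed elsewhere: rotation is not settled between the two texts. The documents simply do not say whether posture affects the sample.

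What remains is a fixed, unsupported position for a research-only procedure, a conflict between two texts meant to match, and a risk section one swab short.

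**Conclusion.** The point holds as a cheap safety improvement with a document conflict attached. The sheet prescribes a position that plausibly makes a participant less steady, the manual does not ask for it, and the risk section leaves this swab out. Up to 108 self-collections are exposed. The probability of a fall cannot be derived from the documents, which give neither a fall rate nor an age range, and no estimate is offered.

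The conclusion rests on two assumptions: that a raised foot with both hands in use is less steady than a supported position, and that an adequate sample can be taken without it, as section 7.2.4 implies. It has no bearing on randomization. All three arms are given the same sheet, so nothing in the texts suggests that the rotation conflict would act differently by arm; its likely cost is uneven sampling. The priority is low, but so is the effort.

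**What to change.** 1. Reword Appendix 2 step 5 so that participants may use any stable, supported position, with either hand.
2. Reconcile Appendix 2 and section 7.2.4 on posture and rotation so that all rectal samples are taken one way. The study team and laboratory should decide the rotation; the documents give no basis for preferring either.
3. Add the rectal swab to section 11.3.1.
4. Check that the consent form describes the rectal swab and its risks, and amend it only if it does not.
5. If collection has started, record the date of the change so that samples taken before and after can be told apart.

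The cost is a few lines of text and a minor ethics notice. The downside is that posture will vary between participants. The documents give no reason to expect this to matter for the sample, but they do not exclude it.

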**Appendix 3. DEQ-5 Questionnaire**
**DEQ 5**
**1. Questions about EYE DISCOMFORT:**

a. During a typical day in the past month, how often did your eyes feel discomfort?

0 	Never
1 	Rarely
2 	Sometimes
3 	Frequently
4 	Constantly

b. When your eyes felt discomfort, how intense was this feeling of discomfort at the end of the day, within two hours of going to bed?

Never have it	Not at all intense	Very intense			
0 	1 	2 	3 	4 	5 

**2. Questions about EYE DRYNESS:**

a. During a typical day in the past month, **how often** did your eyes feel dry?

0 	Never
1 	Rarely
2 	Sometimes
3 	Frequently
4 	Constantly

b. When your eyes felt dry, **how intense was this feeling of dryness** at the end of the day, within two hours of going to bed?

Never have it	Not at all intense	Very intense			
0 	1 	2 	3 	4 	5 

**3. Question about WATERY EYES:**

During a typical day in the past month, **how often** did your eyes look or feel excessively watery?

0 	Never
1 	Rarely
2 	Sometimes
3 	Frequently
4 	Constantly

Score:	1a	+	1b	+	2a	+	2b	+	3	=	Total
	_____	+	_____	+	_____	+	_____	+	_____	=	_____

**Appendix 4. SPEED Questionnaire**
**SPEED™ QUESTIONNAIRE**

Name: \_\_\_\_\_ Date: \_\_\_\_/\_\_\_\_/\_\_\_\_ Sex: M F (Circle) DOB: \_\_\_\_/\_\_\_\_/\_\_\_\_

For the Standardized Patient Evaluation of Eye Dryness (SPEED) Questionnaire, please answer the following questions by checking the box that best represents your answer. Select only one answer per question.

